Protocol Number: LP-CT-PALO-202002

Study Title	A Randomized, Dose-ranging, Open-label, Parallel Group Study to Assess the Efficacy, Safety and Pharmacokinetics of Palonosetron HCl Buccal Film versus IV Palonosetron 0.25 mg (ALOXI®) for the Prevention of Chemotherapy-induced Nausea and Vomiting in Cancer Patients Receiving Moderately Emetogenic Chemotherapy
NCT Number	NCT04592198
Protocol Number	LP-CT-PALO-202002
Protocol Version	2.0
Protocol Date	12 August 2020

SYNOPSIS

Study Number:	LP-CT-PALO-202002
Name of Investigational Product:	Palonosetron HCl Buccal Film (LP035)
Title of Study:	A Randomized, Dose-ranging, Open-label, Parallel Group Study to Assess the Efficacy, Safety and Pharmacokinetics of Palonosetron HCl Buccal Film versus IV Palonosetron 0.25 mg (ALOXI®) for the Prevention of Chemotherapy-induced Nausea and Vomiting in Cancer Patients Receiving Moderately Emetogenic Chemotherapy
Indication:	Prevention of acute and delayed nausea and vomiting associated with moderately emetogenic cancer chemotherapy
Development Phase:	2
Objectives:	To compare the efficacy, safety and pharmacokinetics of single dose of Palonosetron HCl Buccal Film 0.25 mg or 0.5 mg to IV palonosetron 0.25 mg in the prevention of chemotherapy-induced nausea and vomiting in cancer patients receiving moderately emetogenic chemotherapy
Study Population:	The study population will consist of male or female adult chemotherapy naïve (i.e. no history of cytotoxic chemotherapy) or non-naïve patients with histologically or cytologically confirmed solid tumors, scheduled to receive MEC.
Study Design:	This is a randomized, open-label, multicenter, parallel group, dose-ranging efficacy, safety and pharmacokinetic study. Patients will be randomized into three treatment groups.
Number of Subjects:	22 subjects will be randomized into three treatment groups, 8 subjects in 0.25 mg LP035 group, 8 subjects in 0.5 mg LP035 group, 6 subjects in 0.25 mg ALOXI® group. Palonosetron PK will be assessed in a subgroup of patients in 12 patients, 4 patients per group.

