Statistical Methods:	
Efficacy: The primary analysis will be summarized by treatment arm. The number and proportion of patients will be presented by frequency table. For the response rate and for the difference in response rate between each Palonosetron HCl Buccal Film group and IV palonosetron group, 95% confidence interval (CI) will be provided. For the CR rate at 24 h, analyses will be carried out for both FAS and PP population; the other parameters will be analyzed only for FAS population. The subgroups will be analyzed based on FAS for the primary efficacy by age, gender, chemotherapy history, ethanol use, history of pregnancy-related morning sickness, history of motion sickness. The between-group treatment effect (with a nominal 95% CI) for the primary endpoint will be estimated within each category.
 
Safety: The analysis of safety will be performed for the safety set. The result will be interpreted in a descriptive manner. Incidence of AEs will be calculated overall, by system organ and by preferred term. Physical examination, vital signs, 12-lead electrocardiogram and application site evaluation data will be listed and summarized. For vital signs, differences will be calculated compared to baseline. Laboratory data will be analyzed and described considering the age and/or gender dependent normal ranges of the local laboratory. Laboratory data will be summarized and listed. Marked abnormalities and assessments concerning clinical relevance for abnormal values will be included. Shift tables will be used for vital signs and laboratory data to evaluate categorical changes with respect to normal ranges.

Sponsor:	Xiamen LP Pharmaceutical Co., Ltd.

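### Does a trial labelled dose-ranging need a pre-specified comparison of the 0.5 mg film with the 0.25 mg film?

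*Combined protocol and SAP*

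**What the plan says.** The title begins "A Randomized, Dose-ranging, Open-label, Parallel Group Study to Assess the Efficacy, Safety and Pharmacokinetics", and the Study Design row of the Synopsis repeats the label: "This is a randomized, open-label, multicenter, parallel group, dose-ranging efficacy, safety and pharmacokinetic study". Under Number of Subjects, "22 subjects will be randomized into three treatment groups": 8 on the 0.25 mg film, 8 on the 0.5 mg film and 6 on IV palonosetron, with pharmacokinetics measured in 4 patients per group.

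The Objectives row sets the aim as a comparison of "single dose of Palonosetron HCl Buccal Film 0.25 mg or 0.5 mg to IV palonosetron 0.25 mg". It covers efficacy, safety and pharmacokinetics, and it does not mention comparing one film dose with the other.

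Statistical Methods (Efficacy) plans a frequency table of complete response by arm, a 95% interval for each arm's rate, and a 95% interval for "the difference in response rate between each Palonosetron HCl Buccal Film group and IV palonosetron group". The subgroup sentence refers to a between-group effect without naming the groups. Statistical Methods has an Efficacy part and a Safety part but none for pharmacokinetics. Elsewhere the Synopsis defines a pharmacokinetic analysis set and lists the parameters (AUC, Cmax and others).

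**The concern.** A dose-ranging phase 2 trial normally helps to decide which dose goes forward, so one expects the doses to be compared with each other. Here only two of the three possible pairwise differences receive an interval, and the one left out is film against film.

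The two planned differences share the same 6 IV patients, so their errors are positively correlated. A reader who combined the two reported intervals as if they were independent would overstate the uncertainty about the dose effect.

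The pharmacokinetic side looks worse. Comparing pharmacokinetics is part of the objective, and exposure is probably the more informative evidence on dose in so small a trial, yet no analysis is described. Read literally, the plan would report no dose contrast for either response or exposure.

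**Working it through.** **Inputs.** From Number of Subjects: 8 + 8 + 6 = 22 randomized, and 3 × 4 = 12 in the pharmacokinetic subgroup; both totals agree with the text. The documents give no expected response rate, power, margin or pharmacokinetic variability. Response rates of 0.5 to 0.9 and between-subject CVs of 30% to 50% are therefore assumptions.

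**1. Precision of the omitted contrast.** With a common response rate p, the Wald 95% half-width is 1.96 × √[p(1−p)(1/n₁ + 1/n₂)].

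| Assumed p | Film v film (8 v 8) | Film v IV (8 v 6) |
|---|---|---|
| 0.5 | ±49 points | ±53 points |
| 0.6 | ±48 | ±52 |
| 0.7 | ±45 | ±49 |
| 0.8 | ±39 | ±42 |
| 0.9 | ±29 | ±32 |

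The ratio of standard errors is √(1/8 + 1/8) / √(1/8 + 1/6) = 0.926. The film contrast is thus 7.4% tighter, but only if response is similar in all arms. With film at 70% and IV at 90%, the film contrast has variance 2 × 0.21/8 = 0.0525, and film against IV has 0.21/8 + 0.09/6 = 0.0413, so the order reverses.

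**2. The shared IV arm.** At p = 0.8, treating the two film–IV differences as independent gives √2 × 42.3 = 60 points instead of 39. The inflation is √[(1/8 + 1/6)/(1/8)] = 1.53. This affects only a reader who works from the two difference intervals and ignores the counts by arm, which the plan also reports.

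**3. Recovering the dose difference from planned output.** Newcombe 95% intervals computed from counts alone:

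- 6/8 v 6/8: 0 (−38.5 to +38.5 points)
- 7/8 v 5/8: +25 (−17.0 to +58.5)
- 8/8 v 5/8: +37.5 (−2.7 to +69.4)
- 8/8 v 4/8: +50 (+6.8 to +78.5)

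Of these four outcomes, only the most extreme excludes zero.

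**4. Could the contrast choose a dose?** With true rates of 0.6 and 0.8 and 8 per arm, power at the two-sided 5% level is about 13% by the normal approximation and about 5% by exact Fisher test. About 82 per arm would be needed for 80% power.

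**5. Pharmacokinetics.** With 4 per group, the 90% interval for a log-scale difference is ± t × √(1/4 + 1/4) × s.

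- One three-group model (9 df): 1.833 × 0.7071 = 1.296.
- Separate pairs (6 df): 1.943 × 0.7071 = 1.374.
- Ratio 0.943, a 5.7% narrowing. It requires the same log-scale variance for a buccal film and an IV bolus, which the documents do not support with any figure.

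If the observed 0.5/0.25 mg geometric mean ratio were 2.0, then with s = √ln(1 + CV²) and the 9-df multiplier the 90% interval would be about 1.4 to 2.9 at a CV of 30%, 1.2 to 3.3 at 40% and 1.1 to 3.7 at 50%. Using the two film groups alone at 50% (s = 0.472), the limits are 2.0 × exp(±1.374 × 0.472), or 1.05 to 3.83. The choice of model changes little.

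**The case for a change.** The strongest case for a change is the pharmacokinetic one. It does not depend on how the dose-ranging label is read: the objective names a pharmacokinetic comparison, samples are taken from 12 patients, and no method is stated. As step 5 shows, exposure could separate the doses where response could not. Adding a line on each comparison would cost nothing in patients or data, and it would fix the interval method in advance.

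The facts in that argument stand. What does not follow is that the results would suffer. The parameters and the analysis set are already defined, and log-scale geometric mean ratios are the routine summary of AUC and Cmax, so a competent analyst would hardly do otherwise. The posted text is also a synopsis and visibly abridged: the efficacy methods refer to other parameters, although only one efficacy endpoint is listed. It supports saying that the method is not specified here, but not that no comparison will be made.

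For response, testing two doses each against a common reference is an ordinary meaning of dose-ranging, and it is what the objective describes.

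**Conclusion.** No change is called for. The omission is correctly observed, but the planned response contrasts answer the written objective, and only the dose-ranging label points to anything more. The film 0.5 mg minus 0.25 mg difference can be computed from the counts by arm that the plan already reports, and its interval of roughly ±29 to ±49 points could not settle a choice of dose. The 60-point figure describes a misuse of the output rather than a consequence of the plan. The missing pharmacokinetic method is a gap in a synopsis that standard practice fills.

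This rests on assumed response rates of 0.5 to 0.9 with similar response across arms, on Wald approximations at 6 to 8 patients per arm, and on assumed CVs of 30% to 50%. None of these figures is in the documents. A sponsor who wished to list the dose difference and a pharmacokinetic summary could do so as optional reporting, described as imprecise and without claiming a gain from pooling variance across film and IV.

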Study Duration:	Patients not included in the PK subgroups, will stay on the study for a maximum of 16 days including an up to 7-days screening period, 6 days on study (control phase) and a follow-up patient visit or telephone call 3 days after control phase. Patients involved in the PK subgroups will stay on the study for a maximum of 18 days including an up to 7-days screening period, 8 days on study (6 days control phase, and an additional 2 days PK phase) and a follow-up patient visit or telephone call 3 days after the PK phase.
Treatment Groups:	Divided into 3 groups: Test Drug (Group A): Palonosetron HCl Buccal Film 0.25 mg, administered on Day 1, 8 subjects; Test Drug (Group B): Palonosetron HCl Buccal Film 0.5 mg, administered on Day 1, 8 subjects; Reference (Group C): IV palonosetron 0.25 mg (ALOXI®), administered on Day 1 6 subjects.
Criteria for Inclusion:	For inclusion in the study, patients must fulfill all of the following criteria: 1. Provide written informed consent; 2. Male or female, aged ≥ 18 years; 3. With histologically or cytologically confirmed malignant disease; 4. Patients and patients' partners using reliable contraceptive measures;

Criteria for Inclusion:	5. Female patient of childbearing potential having a negative serum pregnancy test; 6. Be able to read, understand, and follow the study procedures and able to complete patient diary autonomously.

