Exclusion Criteria:	Any of the following is regarded as a criterion for exclusion from the study: 1. Expect to be non-compliant with the study procedures; 2. Receive any investigational drugs within 30 days before the start of study treatment or schedule to receive a highly or moderately emetogenic chemotherapeutic agent; 3. Have a clinically unstable seizure disorder with seizure activity requiring anticonvulsant medication; 4. Have severe renal or hepatic impairment; 5. Have positive serology test results; 6. Have a known contraindication to 5-HT ₃ receptor antagonists; 7. Treat with commercially available palonosetron formulations within 2 weeks prior to start of study treatment or enrollment in a previous trial investigating palonosetron; 8. Is allergic to palonosetron or any other 5-HT ₃ antagonist; 9. Is currently a user of any recreational or illicit drugs (including marijuana) or has current evidence of drug or alcohol abuse or dependence as determined by the investigator; 10. Will be receiving stem cell rescue therapy in conjunction with study related course of emetogenic chemotherapy; 11. Has received or will receive total body irradiation or radiation therapy to the abdomen (includes the level of the diaphragm and below) or pelvis in the week prior to Treatment Day 1 and/or during the diary reporting period.
Study Treatments:	Test Drug (Group A): Administration of Palonosetron HCl Buccal Film 0.25 mg on Day 1, 60 ± 10 min before start of Chemotherapy. Test Drug (Group B): Administration of Palonosetron HCl Buccal Film 0.5 mg on Day 1, 60 ± 10 min before start of Chemotherapy. Reference (Group C): IV palonosetron 0.25 mg (ALOXI®) administered on Day 1, 30 ± 5 minutes before start of Chemotherapy, as an IV bolus over 30 seconds.
Schedule of Patient Visits:	Patients will undergo the following visits: 
Screening: Visit 1 (Day -7 to Day -1);Visit 2 (Day 1): chemotherapy and study drug administration;Visit 3 (Day 2): 24 hours after the start of chemotherapy administrationVisit 4 (Day 6 [+2 days]/Day 8): 120 [up to 175] hours after start of chemotherapy administrationVisit 5 (Day 9 [± 1 day]/Day 11 [± 1 day]): follow-up [visit or phone contact].

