Chemotherapy Regimens:	Any MEC (ASCO Guideline), taken on Day 1 is allowed. If more than one agent considered as MEC is administered on Day 1, the start time of the first agent is to be considered as the start of chemotherapy. Any chemotherapy agent of high or moderate emetogenicity during the period from Day 2 up to 120 hours after start of chemotherapy is not allowed.

Efficacy Assessments:	
Primary Endpoint: Complete response (CR) (no emetic episode and no rescue medication) during the first 24 hours after chemotherapy.

Safety Assessments:	Safety assessments include the recording and assessing of all adverse events (AEs), vital signs, physical examinations (PE), clinical laboratory parameters, 12-lead electrocardiogram (ECG), buccal application site evaluation at 0.5 hour (for all subjects), 24 hours (for all subjects) post-dose and at Visit 4 (day 8 for PK subgroups, day 6-8 for non-PK subgroups).
Analysis Sets:	
The full analysis set (FAS) is defined as all randomized patients who received the study medication and at least chemotherapy. The analysis based on the FAS is considered as primary analysis for all efficacy parameters.
 
The per-protocol (PP) set is defined as all patients who completed Day 2 (primary endpoint) and who is compliant with the study protocol.
 
Pharmacokinetic set (PKS) is defined as all subjects completing the study and for whom the pharmacokinetic profile can be adequately characterized.
 
The safety set (SS) is defined as all patients treated and have at least one safety assessment after treatment. "Patients treated" is defined as any patient who received any study medication (palonosetron).

Pharmacokinetic:	Parameters: AUC _{0-t} , AUC _{0-inf} , C _{max} , Residual area, T _{max} , T _{1/2 el} , and k _{el} .

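### Does the synopsis leave the efficacy analysis open by mentioning further efficacy parameters that it does not list?

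*Combined protocol and SAP*

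**What the plan says.** Three places in the Synopsis bear on which efficacy parameters exist.

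- Efficacy Assessments has a single entry, the primary endpoint: "Complete response (CR) (no emetic episode and no rescue medication) during the first 24 hours after chemotherapy".
- Analysis Sets speaks in the plural: "The analysis based on the FAS is considered as primary analysis for all efficacy parameters".
- Statistical Methods, Efficacy, gives the 24-hour response rate an analysis on two sets, then adds that "the other parameters will be analyzed only for FAS population".

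The Indication row is wider than the listed endpoint: "Prevention of acute and delayed nausea and vomiting associated with moderately emetogenic cancer chemotherapy".

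Four places bear on how long patients are observed.

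- Number of Subjects: "Palonosetron PK will be assessed in a subgroup of patients in 12 patients, 4 patients per group", within groups of 8, 8 and 6.
- Study Duration gives PK patients "8 days on study (6 days control phase, and an additional 2 days PK phase"), against 6 days for the others.
- Schedule of Patient Visits places Visit 4 at 120, and up to 175, hours after chemotherapy starts. Safety Assessments puts it on day 8 for PK patients and on days 6 to 8 for the rest.
- Chemotherapy Regimens says that a further agent of high or moderate emetogenicity "during the period from Day 2 up to 120 hours after start of chemotherapy is not allowed". The radiotherapy exclusion criterion mentions a diary period of unstated length: "in the week prior to Treatment Day 1 and/or during the diary reporting period".

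**The concern.** An analysis rule for parameters that are never named looks like an unfinished plan. The indication includes nausea and the delayed phase. The only listed endpoint covers the first 24 hours and is built from emesis and rescue medication. In an open-label study of 22 patients, a reader of the synopsis cannot tell which delayed-phase or nausea results were intended and which might be picked once the data are in.

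The missing window adds to this. Three times in the synopsis could be taken as the end of a delayed phase: 120 hours, Visit 4, or the end of the diary period. If Visit 4 were used, PK patients could be observed longer than the others, and they make up a larger share of the IV arm. More time at risk gives more chance of an emetic episode or rescue, which would count against the comparator.

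There is also a wording point. The primary endpoint counts from chemotherapy, without saying whether from its start or its end, while the dosing times, Visits 3 and 4 and the 120-hour limit all refer to the start.

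**Working it through.** **Step 1: the study's own figures agree.** Groups: 8 + 8 + 6 = 22. PK subgroup: 3 × 4 = 12. Maximum stay: 7 + 6 + 3 = 16 days without PK sampling and 7 + 8 + 3 = 18 days with it. All match the synopsis. The two stays differ only by the 2 PK days; the control phase is 6 days in both.

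**Step 2: are the further parameters named anywhere in the synopsis?** No. The PK parameters cannot be meant, because the sentence stands in the Efficacy paragraph and PK has its own analysis set. The subgroup analyses cannot be meant either, since they concern the primary endpoint. The reference is therefore without a list in this text.

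**Step 3: how large could the observation-time imbalance be?** Suppose a delayed window opens at 24 h and closes at Visit 4. Let p be the PK share of an arm, and let t_PK and t_non be the Visit 4 times of PK and other patients.

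- Mean observed time = p(t_PK − 24) + (1 − p)(t_non − 24).
- p = 4/8 = 0.500 in each film group and 4/6 = 0.667 in the IV group.
- IV minus film = (4/6 − 4/8)(t_PK − t_non) = (t_PK − t_non)/6.

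Day 8 is taken as 7 × 24 = 168 h (an assumption). The 120 and 175 h limits come from the visit schedule. PK patients are assumed to attend no earlier than the others.

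| t_PK (h) | t_non (h) | Film (h) | IV (h) | Difference |
|---|---|---|---|---|
| 168 | 120 | 120.0 | 128.0 | 8.0 h (6.7%) |
| 168 | 144 | 132.0 | 136.0 | 4.0 h (3.0%) |
| 168 | 168 | 144.0 | 144.0 | 0 h |
| 175 | 120 | 123.5 | 132.7 | 9.2 h (7.4%) |

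With a fixed end at 120 h, every patient contributes 120 − 24 = 96 h and the difference is 0.

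**Step 4: which end do the documents support?** 120 h after the start falls on Day 1 + 120/24 = Day 6, the last day of the control phase that all patients share. The limit on further chemotherapy ends at the same hour. Study Duration calls the extra days of PK patients a PK phase, not more control phase. Visit 4 is a window for attendance, and the diary period is mentioned only in an exclusion criterion. Neither is offered as an endpoint window. The common end at 120 h is the natural reading, and it gives the zero row.

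**Step 5: the clock of the primary endpoint.** 24 h after the start falls on Day 1 + 24/24 = Day 2. That is Visit 3, which is timed from the start of chemotherapy. The per-protocol definition also ties the primary endpoint to Day 2. Chemotherapy Regimens fixes the start when several agents are given. A count from the end of the infusion would not be complete at Visit 3. Only one reading fits the schedule.

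**The case for a change.** The best argument for a change is that prespecification is cheap and matters most when treatment is open and numbers are small. With 22 patients and an indication that includes delayed emesis and nausea, an unlisted set of parameters leaves room for selection, and a window tied to Visit 4 would not treat the arms alike. Listing the parameters needs no new patient, visit or test.

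Part of this stands. The synopsis does refer to efficacy parameters without listing them or saying where they are listed, and a pointer would be good housekeeping.

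The rest does not carry. First, the text available is a synopsis. Its silence does not show that the full protocol lacks the list. Second, the 4 to 9.2 hour imbalances belong to an endpoint that no section defines, and the largest needs every PK patient seen at 175 h and every other patient at exactly 120 h. Third, labelling such results exploratory would remove nothing: the efficacy analysis is frequency tables with 95% confidence intervals, and no hypothesis test, margin or success criterion is stated. Fourth, the wording of the primary endpoint is not the sole exception to a uniform clock. The application-site checks count from dosing, and the 24-hour response rate in Statistical Methods has no anchor at all. Uneven wording of this kind is common in a synopsis and misleads no one here.

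**Conclusion.** No change to the plan is needed. The observation is accurate: further efficacy parameters are mentioned, and none is named or given a window in the synopsis. It is missing detail in a summary, together with a clerical omission of the start of chemotherapy in the endpoint.

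The primary 24-hour analysis is fully identified by its endpoint, analysis sets and interval estimates, and it is untouched. For any delayed-phase summary, the difference in observation time between arms is 0 h under the common 120 h end to which the control phase and the chemotherapy limit point. It could reach 9.2 h only under a window that the plan does not state. An analyst following the synopsis would count from the start of chemotherapy, stop at 120 h, use the FAS, and report descriptively.

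This rests on two assumptions: that the PK days do not count as efficacy observation, which their separate label supports, and that no confirmatory claim is attached to the unlisted parameters, which agrees with the absence of any stated test. Whether the full protocol lists them cannot be judged from this text.

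### Do subgroup confidence intervals from arms of 8, 8 and 6 need to be removed from the plan?

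*Combined protocol and SAP*

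**What the plan says.** The Number of Subjects entry in the Synopsis sets the arms at "8 subjects in 0.25 mg LP035 group, 8 subjects in 0.5 mg LP035 group, 6 subjects in 0.25 mg ALOXI® group". Subgroups are analysed in the full analysis set, which the Analysis Sets entry limits to randomized patients: "The full analysis set (FAS) is defined as all randomized patients who received the study medication and at least chemotherapy". The arm sizes are therefore upper limits.

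Under Statistical Methods (Efficacy), the main result is plain: "The primary analysis will be summarized by treatment arm", and for the "difference in response rate between each Palonosetron HCl Buccal Film group and IV palonosetron group, 95% confidence interval (CI) will be provided". The primary endpoint is then broken down "by age, gender, chemotherapy history, ethanol use, history of pregnancy-related morning sickness, history of motion sickness", with the commitment that "The between-group treatment effect (with a nominal 95% CI) for the primary endpoint will be estimated within each category".

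The text gives no category cut-points, interval method, minimum cell size or rule for an empty cell. It also attaches no hypothesis test, margin, power claim or decision rule to these intervals.

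**The concern.** The plan promises an effect and an interval in every category of six factors from 22 patients. Three things look wrong.

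- The cells are so small that most intervals will span most of the range anyone would consider plausible.
- If one arm has nobody in a category, the difference does not exist, so a promise covering each category may be impossible to keep.
- No interval method is named, and methods disagree sharply at this size. A simple Wald interval collapses to zero width when everyone in both cells responds.

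At stake would be a set of subgroup contrasts that cannot be produced in full, and a risk that a chance exclusion of zero is read as a finding.

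**Working it through.** **Inputs.** Arms of 8 (film 0.25 mg), 8 (film 0.5 mg) and 6 (IV) come from Number of Subjects. The six factors and the nominal 95% level come from Statistical Methods. Two categories per factor, the category prevalences and the CR rates are assumptions, because the documents give none. The film-versus-IV contrast is carried over from the sentence on the whole arms; the subgroup sentence says only between-group.

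**The plan's own figure.** 8 + 8 + 6 = 22, as stated. There is no power or precision calculation to reproduce.

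**Number of intervals.** 6 factors × 2 categories × 2 contrasts = 24. Six IV patients split two ways leave at most 6/2 = 3 in the smaller cell.

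**Width.** The Newcombe interval for d = p1 − p2 uses the Wilson limits (l, u) of each proportion:

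- lower = d − √[(p1 − l1)² + (u2 − p2)²]
- upper = d + √[(u1 − p1)² + (p2 − l2)²]

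Whole arms, 6/8 versus 4/6: the Wilson limits are 0.409 to 0.929 and 0.300 to 0.903, and d = 0.083.
- lower = 0.083 − √(0.341² + 0.237²) = −0.33
- upper = 0.083 + √(0.179² + 0.367²) = +0.49
- width: 82 points

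Half arms with the same observed rates, 3/4 versus 2/3: the Wilson limits are 0.301 to 0.954 and 0.208 to 0.939.
- lower = 0.083 − √(0.449² + 0.272²) = −0.44
- upper = 0.083 + √(0.204² + 0.459²) = +0.59
- width: 103 points

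| Cell sizes (film v IV) | Width over all outcomes (points) | Expected width, common CR 50–90% (points) |
|---|---|---|
| 8 v 6 (whole arms) | 51–85 | 76–82 |
| 6 v 4 | 63–94 | 90–91 |
| 4 v 3 | 75–105 | 100–104 |
| 2 v 1 | 103–145 | 127–139 |

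At 4 versus 3, Newcombe excludes zero only for 4/4 v 0/3, 3/4 v 0/3 and their mirror images 0/4 v 3/3 and 1/4 v 3/3. At 4/4 v 3/3 it gives −49 to +56 points, where Wald gives zero width.

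**Empty cells.** Let p be the share of patients in one category. For one factor, the chance that some arm has an empty category is

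e = 1 − [1 − p⁸ − (1−p)⁸]² × [1 − p⁶ − (1−p)⁶].

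Over six independent factors it is 1 − (1 − e)⁶. The expected number of inestimable contrasts is 6 × 2 × the sum over both categories of [1 − (1 − q⁸)(1 − q⁶)], where q is the chance that a patient lies outside the category.

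| p | e | At least one empty cell, six factors | Expected inestimable contrasts of 24 |
|---|---|---|---|
| 0.5 | 0.046 | 25% | 0.5 |
| 0.3 | 0.217 | 77% | 2.0 |
| 0.2 | 0.489 | 98% | 4.6 |

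A latent correlation of 0.3 to 0.6 between factors lowers the three chances to 21–24%, 64–72% and 92–96%.

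**What this shows.** Even at p = 0.2, 24 − 4.6 = 19.4 contrasts on average can still be computed. From the whole arms to a half split, the interval widens by 103/82 = 1.26 times. The subgroup intervals are worse than the main ones, but the main ones are already very wide.

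**The case for a change.** The strongest case for a change is that the sponsor has committed to output that may not be producible in full and will say little where it is. Counts of responders by category and arm would show the same data without suggesting that an effect can be estimated. The label nominal deals with multiplicity; it does not deal with empty cells or with the unnamed method. The change would cost only a few words.

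The facts in that case stand: the widths, the ceiling of 3 IV patients, and the likelihood of empty cells when categories are uneven. Its consequence does not.

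- An empty cell is ordinarily reported as not estimable, and no reader is misled by that.
- An interval 100 points wide states the lack of information more clearly than a bare 3/4 versus 2/3.
- The supplied text is a synopsis. The interval method, the cut-points and a sparse-cell rule are details that an analyst settles when writing the table shells. So is tabulating morning-sickness history only among women with a prior pregnancy.
- The zero-width result needs Wald, which the plan does not name.
- The chance that at least one of 24 intervals excludes zero with no true effect cannot be sized. It runs from 1% (Fisher-type, assumed CR 90%) to 97% (Wald), depending on the method and the assumed rates.

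Statisticians could reasonably delete the intervals, keep them as exploratory, or show them only above a minimum cell size. That is a choice of presentation, and nothing in the trial's conclusions turns on it.

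**Conclusion.** The observation is correct, but it does not call for a change. About 24 subgroup intervals are planned, with Newcombe widths of 75 to 105 points at 4 versus 3 patients. On average 0.5 to 4.6 of them would be inestimable at prevalences of 50% down to 20%. The whole-arm comparison is itself 51 to 85 points wide in this phase 2, dose-ranging study of 22 patients, so the subgroup rule adds to an imprecision that the design already carries.

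The intervals feed no test, margin or decision, and the primary by-arm CR summary is unaffected. Removing them would change no estimate and no conclusion, and the unstated method and sparse-cell rule are gaps that analysts fill sensibly.

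This rests on two categories per factor, film-versus-IV contrasts within subgroups, and assumed prevalences and CR rates. The 4-versus-3 widths and the 3-patient IV ceiling do not depend on the prevalences or CR rates.
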